In the study of Mazza et al. (2121), the presence of psychopathology (mainly depressive symptomatology) was shown to significantly influence neurocognition in post-COVID patients, most notably affecting verbal fluency, information processing, and executive functions at one and/or three months assessments. Patients' sex,

previous psychiatric diagnosis, and duration of hospitalization for COVID-19 did not significantly affect the neurocognitive function (7).

Importantly, preliminary findings of the same research group indicate that the observed cognitive deficits worsen between three- and six-month follow-up (Figure 1, unpublished data). Furthermore, the neurocognitive profile of these patients demonstrates some similarities with patterns observed in depressed patients using the same assessment method. Yet whereas the depressed symptoms of post-COVID NP patients seem to respond well to regular treatment with serotonergic antidepressants, the cognitive symptoms do not.

[figure not shown]

Figure 1: Cognitive profile of post-COVID patients compared to Healthy controls (HC) and depressed patients (MDD) (Mazza et al. 2021, *in prep*) (7)

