1.3. Immune disturbances as translational pathways

1.3.1. Systemic immunological disturbance

Large population cohort studies have replicated the finding of systemic immune disturbances (such as but not limited to IL-6 and C-reactive protein (CRP)) in cohorts of patients with depression (19). Longitudinal studies demonstrated the predictive value of these immunomarkers towards clinical outcome and the development of comorbidities such as chronic fatigue, anorexia, insomnia, somatic disease, ... (20–23). Anti-inflammatory agents have been confirmed as valid add-on treatment options to improve depressive symptoms (24). In longitudinal analyses, higher baseline IL-6 levels predicted a subsequent chronic course of depression in women but not in men (25). Similarly, higher baseline IL-6 levels in childhood were associated with depressive and psychotic symptoms at age 18 (26).

Finally, the clinical observation that some patients with long COVID complaints experience an improvement of their NC symptoms following SARS-CoV-2 reinfection or vaccination supports the hypothesis of immune-related pathways involved in the pathophysiology of post-COVID NP complications.

[figure not shown]

Figure 2: Effect of the decrease of systemic inflammation from hospital admission to 3 months follow-up on the pattern of change of depressive symptoms (measured with BDI-13) during follow-up. (7)

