- Pre-existing neurological diseases

[figure not shown]

Figure 3: Flowchart of the COVID-19 participant inclusion and the work packages (WP). Participants with a confirmed positive PCR test will be included at UZA or UPCD and are classified in the patient group when suffering from neuropsychiatric symptoms for more than 4 weeks. All participants undergo psychiatric assessment and blood sampling on every time point of the study (WP1). Additionally, if patients do not fulfill the exclusion criteria for HPA-axis assessment (pregnancy, breastfeeding, treatment with corticosteroids, hormonal replacement therapy with exception of contraceptives), they are included in the cortisol subgroup (WP2). Finally, all participants, except those treated with class III drugs according to the DRUID classification, those suffering from pre-existing neurological disease or substance abuse and those with an IQ below 90, undergo neurocognitive assessment (WP3).

[figure not shown]

Figure 4: Flowchart of the healthy control inclusion and the work packages (WP). Healthy volunteers can be included in Cb if they were not infected with Sars-CoV-2 in the past and if they do not complain from psychic or cognitive symptoms. If they meet the exclusion criteria for the cortisol testing, they are excluded from the study. WP2 is only performed at baseline.

Study design

General study design:

This is a longitudinal study, which will be organized into three work packages (WP1, WP2 and WP3). Enrollment will continue for an estimated period of 24 months, depending on the time course of the epidemic curve. Last-patient-in is expected no later than November 1st, 2023.

Patients will be referred mainly by the University Hospital of Antwerp (UZA) and enrolled at first visit to the University Psychiatric Hospital (UPCD), where follow-up will also take place at 3, 6 and 12 months. Patients can also be referred by the Flemish long COVID patient support group.

Sample size:

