Based on current referral rates, we expect on average 1-2 new referrals each week. After 12 months, we expect a total of ± 50 patient inclusions. In a MANOVA analysis, a total sample size of 64 offers 80,0% power to detect a medium sized effect ($f^2 \geq 0.15$). We aim for a total sample size of 130 in order to achieve higher effect sizes and to maintain sufficient power in the subgroup analyses and in case of missing values. As Ca is the main control group for the long COVID patient group, these two groups are of equal size (both 50 participants). We included a smaller Cb group to compare the immunological blood parameters between healthy volunteers and long COVID patients.

Study visits:

As part of routine clinical care, patients will receive psychiatric evaluation at the University Hospital Campus UZA, and neurocognitive evaluation at Campus Duffel. During the clinical evaluations, participants will be invited to participate in the study. If they are interested, they will be invited to a baseline visit assessing eligibility and covering informed consent procedure. In order to adhere to social distancing regulations, it may occur that this baseline visit is held digitally via livestream/webcam or by telephone. In this case, patients sign their ICF digitally. To ensure patient privacy, only in-house fully secured internet and telephone connections will be used for distanced baseline visits.

Once included, the participant will be invited for the baseline assessment, which includes a broad neuropsychological examination. A blood sample will be collected at each time point during the study.

	SCREENING	BASELINE	3 MONTHS	6 MONTHS	12 MONTHS
PATIENT GROUP	Eligibility, psychiatric and IQ screening	Psychiatric assessment Blood sample	Psychiatric assessment Blood sample	Psychiatric assessment Blood sample	Psychiatric assessment Blood sample
+ NC SUBGROUP		Neurocognitive assessment		Neurocognitive assessment	
+ HPA SUBGROUP		Saliva sample		Saliva sample	
CONTROL GROUP A	Eligibility, psychiatric and IQ screening	Psychiatric assessment Blood sample	Psychiatric assessment Blood sample	Psychiatric assessment Blood sample	Psychiatric assessment Blood sample
+ NC SUBGROUP		Neurocognitive assessment			
+ HPA SUBGROUP		Saliva sample			

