3.5. Statistical analysis

CAPRI has ongoing collaborations with StatUA and BIOMINA for statistical analyses of past and ongoing projects involving biomarker-data. In this project, we will study cross-sectional and bidirectional longitudinal associations between *NP symptoms* and *Inflammation* or *Insomnia* (cfr above).

To study the cross-sectional association using all available data, we will stack data from all timepoints in one cross-sectional dataset. To account for the fact that one person can have multiple observations in this combined cross-sectional dataset, we will analyze the association between NP symptoms and inflammation / insomnia (measured at the same timepoint) using linear mixed models with timepoint as repeated effect and patient identifier as within-subject effect and using an unstructured correlation matrix. Estimates from this model thus represent the cross-sectional association between predictor and outcome.

For longitudinal analyses the effect of baseline *Inflammation* and *Insomnia* on *NP symptoms* at 3- and 6-month follow-up will be evaluated using linear mixed models with time as repeated effect and patient identifier as within-subject effect and using an unstructured correlation matrix. Baseline predictor by time interaction (time coded as 0, 3, or 6) will be included to test differences in slope but retained only in models when statistically significant. Treatment group (antidepressant treatment, insomnia treatment, cognitive remediation, a combination, or none) will be included

as predictor. Baseline values of NP symptoms will be included as covariates, and all other covariates measured at baseline as well.

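### The stacked symptom model lists no fixed visit effect, so a trend over follow-up shared by symptoms and predictor would be read as a same-visit association

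*Combined protocol and SAP*

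**What the plan says.** For the cross-sectional question, section 3.5 states that "we will stack data from all timepoints in one cross-sectional dataset". The association between values taken at the same visit is then analysed "using linear mixed models with timepoint as repeated effect and patient identifier as within-subject effect and using an unstructured correlation matrix". No fixed effects other than the predictor are named for this model. The paragraph ends: "Estimates from this model thus represent the cross-sectional association between predictor and outcome".

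The next paragraph, on the longitudinal model, does name terms of the mean: "Baseline predictor by time interaction (time coded as 0, 3, or 6) will be included to test differences in slope", together with treatment group and baseline covariates.

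The general study design text under section 3 has patients enrolled at UPCD, "where follow-up will also take place at 3, 6 and 12 months", so a patient contributes up to four stacked rows. Section 3.4 lists SII, CRP, IL-6 and kynurenine metabolites at baseline and follow-up, and HERV-W-ENV at baseline only.

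**The concern.** A repeated effect and a subject identifier tell the model which residuals are correlated. They do not let the average differ from visit to visit. If the mean part is only an intercept and the predictor, the coefficient mixes two things: the association among people seen at the same visit, and the parallel movement of visit averages over the year. Only the first is the stated target, so the plan's closing claim about what the estimate represents does not follow from the terms it lists.

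Objectives 2 and 3 rest on this model. Insomnia against depression or anxiety is where shared trends are most plausible. Patients enter on positive screening scores (section 3.1). BDI-21, STAI and ISI appear in Table 1 both at screening and during follow-up. Treatment may start after baseline (section 3.3.6), and section 3.5 names both antidepressant and insomnia treatment, but as a predictor only in the longitudinal model. If both scores drift down for unrelated reasons, the link is overstated. If the two variables move in opposite directions, a real link is understated.

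**Working it through.** **The plan's own figure.** None exists for this model. The only power figure (total N of 64, 80.0% power, f² ≥ 0.15) is for a MANOVA. It reproduces as a minimum N of 64 with 80.6% power if one assumes 3 groups, 6 responses and alpha 0.05. It has no bearing on this point.

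**Inputs from the documents.** Visits at 0, 3, 6 and 12 months; 50 patients; unstructured covariance; no listed visit term.

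**Assumptions.** Complete data; two-sided 5% test (no alpha is stated); equal within-person correlation ρ for predictor and outcome; trends in SD units.

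**Step 1: direction and size by formula.** Take unit within-visit variance, a compound-symmetric covariance treated as known, and a true same-visit slope β. Let c be the covariance across visits of the two sets of visit means, and v the variance of the predictor's visit means. The slope without visit means is then approximately

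b = [β(1 − ρ) + c] / (1 − ρ + v).

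For linear trends over 12 months, time runs 0, 0.25, 0.5, 1, with mean 0.4375. Its variance is 1.3125/4 − 0.4375² = 0.1367. If both variables fall 0.5 SD, c = v = 0.25 × 0.1367 = 0.0342. With β = 0:

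- ρ = 0.3: 0.0342/0.7342 = 0.047
- ρ = 0.6: 0.0342/0.4342 = 0.079
- ρ = 0.8: 0.0342/0.2342 = 0.146

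If only one variable trends, c = 0 and b = 0. With opposite 0.5 SD trends, β = 0.20 and ρ = 0.6, b = (0.08 − 0.0342)/0.4342 = 0.105.

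**Step 2: simulation with the unstructured covariance estimated** (iterated GLS, t test on n − 1 df, 1000 runs per row, linear trends, n = 50, no true association). Rejection rates are for ρ = 0.3 / 0.6 / 0.8.

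| Fall in each variable | No visit means | With visit means |
|---|---|---|
| none | 7.3 / 7.5 / 6.1% | 7.7 / 7.8 / 6.7% |
| 0.25 SD both | 5.6 / 7.3 / 10.7% | 5.9 / 6.0 / 7.1% |
| 0.5 SD both | 11.3 / 17.8 / 37.1% | 5.5 / 7.2 / 6.0% |
| 0.5 SD in one only | 7.3 / 6.8 / 6.9% | 8.3 / 6.1 / 7.0% |

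Mean false slopes at 0.5 SD are 0.044, 0.064 and 0.109. These lie below the formula because the estimated covariance absorbs part of the trend as extra variance. The excess over 5% without trends is a small-sample feature of this simple test, not of the plan.

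**Step 3: a front-loaded trend** (60%, 80% and 100% of the fall by 3, 6 and 12 months), n = 50, ρ = 0.5 and 0.7. With 0.5 SD falls in both variables, three sets of runs gave 14.0% and 25.4%, 13% and 25%, and 16% and 26%, against 6-8% with visit means. At 0.3 SD the rate is 7.5-10%.

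**Step 4: opposite trends** (n = 50, ρ = 0.6, linear, true slope 0.20). With 0.5 SD trends the mean slope is 0.129 and power 48.0%; with visit means these are 0.201 and 81.6%.

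**The case against.** **The plan does not exclude a visit term.** It describes how repeated observations are handled and gives no full list of fixed effects, so an analyst could add one. This stands, and it is why the point is worded as what happens if the model is fitted as written. It does not remove the point: the neighbouring paragraph does name mean-model terms, and adding visit later can change which associations are significant.

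**Trends in markers are not documented for this study's follow-up.** The caption of Figure 2, "Effect of the decrease of systemic inflammation from hospital admission to 3 months follow-up on the pattern of change of depressive symptoms", starts at hospital admission, whereas patients here enroll more than 4 weeks after infection. Nobody is selected on a blood marker, so regression to the mean does not act on markers. This stands. A reader might infer that the inflammation results will be spurious; the documents do not support that.

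**Cognition.** A reader might pair the remark that "the observed cognitive deficits worsen between three- and six-month follow-up" with falling inflammation and apply the four-visit power figures. Section 3.3.6 and Figure 5 put patients' repeat testing at 6 months only, so those figures do not carry over. With two visits, power is about 52% even with visit means (12-23% without). Only the direction survives.

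**Insomnia and mood are expected to be truly linked** (section 1.4), so a false-positive rate under no association is less relevant. This is fair, but the estimate is still distorted. With β = 0.20, ρ = 0.6 and parallel 0.5 SD falls, the formula gives (0.08 + 0.0342)/0.4342 = 0.263. Screening also precedes baseline, so some regression to the mean may be over by the first stacked visit.

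**The longitudinal model.** A reader might infer that its slope test fails in the same way. Rejection rates of 43% or 26-28% (predictor mean/SD of 2.5 or 1, common 0.5 SD fall over 6 months) arise only if the interaction is fitted without a time main effect. Testing a difference in slope presupposes a slope, so that is not the natural reading. With the main effect the rate is 5-6%.

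**Conclusion.** The point holds for the stacked model. Its listed terms do not deliver the interpretation that section 3.5 gives the estimate, because shared movement of visit averages enters the coefficient. With 50 patients and four visits, 0.5 SD falls in both variables raise rejection under no association to about 13-26% at within-person correlation 0.5 to 0.7, against about 6-8% with visit means. The excess is small at 0.3 SD or less for those correlations, and absent when only one variable trends.

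These sizes rest on assumed trends and correlations. The support is strongest for insomnia against depression or anxiety, conditional for SII, CRP, IL-6 and kynurenine metabolites, and nil for HERV-W-ENV. The documents do not show that the longitudinal model is wrong; its time main effect only needs confirming. The change should be made before analysis, since it is nearly free and objectives 2 and 3 depend on this model.

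**What to change.** In section 3.5, state that the stacked model includes visit as a categorical fixed effect, in addition to its use as the repeated effect, and describe the estimate as the association adjusted for visit means. If control group Cb is stacked too, give its 1-, 2- and 3-month visits their own visit coding, since a 0/3/6/12-month factor does not fit them. For the longitudinal model, confirm that the time main effect is present whenever the predictor-by-time interaction is tested; centring the baseline predictor is then optional.

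The cost is a sentence or two of wording and up to 3 degrees of freedom (four visits less one) for the 0/3/6/12-month schedule. No new data are needed. The downside is that parallel change of group averages no longer counts as association, so some associations will look weaker.

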Also, long COVID can be regarded as a condition of chronic stress, which could theoretically be associated with disturbances of the hypothalamo-pituitary-adrenal (HPA) axis, although no studies on HPA axis (dys)function in long COVID have been reported yet.

The aims of this study are to describe the standardized evaluation of the psychopathological and neurocognitive function of long COVID patients and their evolution over time; to explore the cross-sectional and longitudinal association

between long COVID symptoms and immunological measures; and to examine the neuro-endocrine (HPA-axis) characteristics of long COVID syndrome.

Three participant groups will be included: 1) long COVID patients with neuropsychological complaints (P), 2) COVID-survivors without persistent complaints (Ca) and 3) healthy volunteers (Cb).

This is a longitudinal study, starting from November 1st 2021. Enrollment will continue for an estimated period of 24 months, depending on the time course of the epidemic curve. Last-patient-in is expected no later than November 1st, 2023. The study will be organized into three work packages (WP1, WP2 and WP3). WP1 includes psychiatric assessments using questionnaires and blood sampling and is the standard WP for every participant. WP2 includes cortisol measurement using saliva sampling for patients and controls from Cb. who do not fulfill specific exclusion criteria (pregnancy, breastfeeding, hormonal therapy with exception of contraceptives, cortisol treatment). Finally, WP3 includes an extensive neurocognitive assessment by a specialized neuropsychologist for both patients and controls from Ca who do not fulfill specific exclusion criteria (sedative medication, pre-existing neurological disease, severe substance abuse, and IQ < 90).

Patients and controls from Ca will be referred mainly by the University Hospital of Antwerp (UZA) and by long COVID patient support groups and enrolled at first visit to UPCD, where follow-up will also take place at 3, 6 and 12 months. WP1 will be performed at each timepoint, while WP2 and WP3 will only be carried out at baseline and 6 months.

Total sample size is estimated on 130 participants.

List of Abbreviations

- ACTH: adrenocorticotrophic hormone
- BACS: brief assessment of cognition in schizophrenia
- BDI: Beck depression index
- Ca: Control group a: COVID-survivors without NP complaints
- CAR: cortisol awakening response
- Cb: Control group b: healthy controls
- CFS: chronic fatigue syndrome

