1.4. Insomnia

Genome Wide Association Studies have demonstrated a strong correlation of the genetic risk of insomnia with depression and anxiety (36,37). Furthermore, insomnia has been identified as a primary risk factor for the onset, persistence and relapse of anxiety, depression and PTSD. In a Network Outcome Analysis of 768 individuals without history of depression, *difficulty initiating sleep* was one of only five direct predictors of first-onset major depressive disorder after six years follow-up (38).

Depending on the study methods, in long COVID patients the prevalence of clinically relevant insomnia was estimated between 5% (diagnosis of insomnia disorder in electronic medical records <6m following infection) and 24% (self-rated insomnia symptoms above clinical cut-off at 3-month follow-up). These symptoms could represent an important risk factor in the subsequent development of anxiety and depressive disorders, and a key mechanism underlying cognitive deficits.

2. Research Objectives

- 1) Describe the standardized evaluation of the psychopathological and neurocognitive function of long COVID NP patients and their evolution over time;
- 2) Explore the cross-sectional and longitudinal association between long COVID NP symptoms and immunological measures;
- 3) Define the prevalence and clinical characteristics of insomnia in long COVID NP patients, as well as its correlation to the clinical psychiatric and neurocognitive symptom domains;
- 4) Compare the immunological profile of long COVID NP patients to those of existing cohorts of comparable primary psychiatric conditions and healthy controls;
- 5) To examine the neuro-endocrine (HPA-axis) characteristics of long COVID syndrome

3. Methodology

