3.3.6. Follow-up measures

Depending on the clinical findings, treatment with psychopharmacological compounds may be initiated or patients may be enrolled in a group cognitive remediation program contingent upon clinical indication. Follow-up visits with psychiatric evaluation, self-rating scales and blood sampling will take place every 3

months for a maximum of one year. Follow-up neuropsychological assessment will take place once after 6 months.

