3.4. Endpoint measurements

“NP symptoms”

- Baseline and follow-up scores on clinical scales of depression, anxiety, and insomnia
- (subgroup) Baseline and follow-up cognitive functioning

“Inflammation”

- Quantitative measurement of HERV-W-ENV in serum at baseline
- Calculation of systemic immune inflammatory index (SII= thrombocyte count x neutrophile count / lymphocyte count) at baseline and follow-up
- Quantitative analysis of CRP and IL-6 at baseline and follow-up
- Quantitative analysis of kynurenine metabolites at baseline and follow-up

(subgroup) *“HPA axis”*

- CAR

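### The stacked mixed model is said to give the cross-sectional association, but for repeatedly measured predictors its single slope is a pooled concurrent association that generally differs from a same-visit slope

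*Combined protocol and SAP*

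**What the plan says.** Section 2 (Research Objectives) sets out to "Explore the cross-sectional and longitudinal association between long COVID NP symptoms and immunological measures". For the cross-sectional part, section 3.5 (Statistical analysis) stacks the data from every visit and states: "we will analyze the association between NP symptoms and inflammation / insomnia (measured at the same timepoint) using linear mixed models". The model takes timepoint as the repeated effect and the patient as the within-subject effect, with an unstructured correlation matrix. The reason given is that one person can contribute several rows. The paragraph ends: "Estimates from this model thus represent the cross-sectional association between predictor and outcome".

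Section 3.4 (Endpoint measurements) makes most of the predictors time-varying, for example "Quantitative analysis of CRP and IL-6 at baseline and follow-up". SII, the kynurenine metabolites and the insomnia scales are likewise measured at baseline and follow-up. The exception is "Quantitative measurement of HERV-W-ENV in serum at baseline".

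Patients and the Ca controls have four visits (baseline, 3, 6 and 12 months). Cognition is measured less often: section 3.3.6 says "Follow-up neuropsychological assessment will take place once after 6 months".

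**The concern.** Modelling the within-person correlation gives appropriate standard errors. It does not settle what the slope measures. A repeatedly measured marker carries two kinds of information: people with higher usual levels may have worse symptoms, and a given person may be worse at the visits where the marker is higher. One slope fitted with correlated residuals averages the two, with weights that depend partly on the residual correlation and the number of visits. A slope taken at a single visit also averages them, but its weights come only from how the marker's variance splits between and within persons. The inference in the last sentence of the cross-sectional paragraph therefore does not follow from what precedes it.

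The protocol's rationale draws on both kinds of association. Its opening summary cites baseline inflammation predicting later depressive severity. The caption of Figure 2 (section 1.3.1) describes the "Effect of the decrease of systemic inflammation from hospital admission to 3 months follow-up on the pattern of change of depressive symptoms". A reader of the Objective 2 results could not tell which of the two a reported slope reflects. The blend also changes with the number of visits, so slopes for symptom scales (up to four visits) and for cognition (at most two) would carry one label but different weights.

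**Working it through.** The plan gives no figure for this slope, so there is none to reproduce. It also gives no intraclass correlations (ICCs), residual correlation or slopes. All four are assumptions below.

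**Set-up.** Marker x = u + e, with total variance 1. The stable part u has variance ICCx and the visit-specific part e has variance 1 - ICCx. The outcome is bs·u + bw·e plus a residual with within-person correlation ICCy. There are T complete visits, equal correlations between visits, and visit intercepts in the model.

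**Formulas.**
- Same-visit slope = bs·ICCx + bw·(1 - ICCx)
- Person-mean slope bb = [bs·ICCx + bw·(1 - ICCx)/T] / [ICCx + (1 - ICCx)/T]
- B = [1 + (T - 1)·ICCx] / [1 + (T - 1)·ICCy]
- W = (T - 1)(1 - ICCx) / (1 - ICCy)
- w = B/(B + W)
- Stacked-model slope = w·bb + (1 - w)·bw

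**Worked case.** ICCx 0.5, ICCy 0.6, bs 0.4, bw 0.2, T = 4:
- B = 2.5/2.8 = 0.893; W = 3 × 0.5/0.4 = 3.75; w = 0.893/4.643 = 0.192
- bb = (0.20 + 0.025)/(0.5 + 0.125) = 0.36
- stacked slope = 0.192 × 0.36 + 0.808 × 0.2 = 0.231
- same-visit slope = 0.20 + 0.10 = 0.300, so the stacked slope is 23% lower

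**Range.** bs is held at 0.4, ICCx runs from 0.3 to 0.9 and ICCy from 0.4 to 0.8. Entries are the stacked slope relative to the same-visit slope.

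| Within-person slope bw | T = 4, ICCs 0.5/0.6 | T = 4, range | T = 2, ICCs 0.5/0.6 | T = 2, range |
|---|---|---|---|---|
| 0 | 0.062 v 0.200 | -17 to -89% | 0.114 v 0.200 | -6 to -74% |
| 0.2 | 0.231 v 0.300 | -8 to -32% | 0.257 v 0.300 | -3 to -23% |
| 0.3 | 0.315 v 0.350 | -4 to -15% | 0.329 v 0.350 | -1 to -10% |
| 0.4 (equal) | 0.400 v 0.400 | 0% | 0.400 v 0.400 | 0% |
| 0.6 | 0.569 v 0.500 | +6 to +26% | 0.543 v 0.500 | +3 to +17% |

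**When the gap closes.** It vanishes when bs = bw and when ICCy = 0. It also shrinks as ICCx approaches 0 or 1: with bw 0.2, ICCy 0.6 and T = 4 it is 9% at ICCx 0.95 and 2% at 0.99.

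**Feedback from symptoms to the marker.** Section 3.5 names bidirectional association as a question, and section 3.3.6 lets treatment start on clinical findings. In a large simulated sample with four visits, ICCs 0.5/0.6 and one true concurrent slope of 0.30, the visit-specific symptom residual was allowed to shift the next marker value by an assumed 0.3 or 0.5 per unit. The per-visit slopes stayed near 0.30. The single stacked slope fell to about 0.26 and 0.24. Splitting the marker gave about 0.33 (person mean) and 0.24 (visit deviation) with feedback 0.3, and 0.36 and 0.21 with feedback 0.5.

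**The case against.** The strongest reply is that the label is clear in context. Predictor and outcome are taken at the same visit, and the next paragraph contrasts this with baseline predictors of later symptoms, so cross-sectional may simply mean concurrent rather than lagged. On that reading the label is loose rather than false, the objective is exploratory, and no confirmatory test is at risk. This stands and limits the point. It does not rescue the inference, because the plan still does not say which concurrent association is estimated.

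A second reply is that the percentages are measured against a same-visit slope that the plan never names as its target, and which itself mixes the two associations. That is fair: the percentages show how far two readings of one label can diverge, not an error against a stated estimand.

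A third reply is that splitting the predictor is no cure. The person-mean coefficient is not the same-visit slope either (0.36 v 0.30 in the worked case). It is imprecise at 50 patients, and feedback can make the two terms differ when the true concurrent slope is common. All of this stands, so the split belongs beside the planned slope and not in its place.

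Finally, the prediction of later severity from baseline inflammation is handled by the separate longitudinal model, which this point does not touch.

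**Conclusion.** The concern holds as a matter of what is estimated and how it is labelled. Allowing for repeated rows does not make the slope cross-sectional. For the repeatedly measured predictors it is a pooled concurrent association that generally differs from a same-visit slope, subject to the exceptions shown in the working. The size cannot be derived from the documents. Under the assumed ICCs and moderately unequal slopes (0.4 v 0.2 to 0.3) the gap is about 4-32% with four visits and 1-23% with two. It is zero if the slopes are equal, and its sign reverses if the within-person slope is the larger.

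Two stronger readings are tempting. A reader might infer that the estimate will be grossly too small, citing the -89% entry. That needs a within-person slope of zero, which the documents do not state and which the relation described under Figure 2 speaks against. A reader might also infer that the planned model is wrong and should be replaced. The documents do not support that either: the model is a reasonable summary of concurrent association, and only the claim about its meaning fails. HERV-W-ENV is not affected because it does not vary over visits, and participants with a single assessment contribute no within-person information.

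**What to change.** 1. Keep the planned single-slope model. Replace its closing sentence with a statement that the slope estimates a pooled concurrent association combining between-person and within-person information.
2. Alongside it, report the same model with each repeatedly measured predictor entered as the person's mean over observed visits and the visit deviation from that mean, both with confidence intervals. Do not choose between the models by a significance test. State that a difference between the two terms is descriptive, because symptoms may influence later marker values.
3. If a same-visit slope is the target, add a working-independence fit with visit as a factor and robust small-sample standard errors, as a sensitivity analysis only.
4. Before fixing the number of cognitive assessments for Ca, reconcile the opening summary ("WP1 will be performed at each timepoint, while WP2 and WP3 will only be carried out at baseline and 6 months", with WP3 covering Ca) with Figure 5, which shows Ca neurocognitive testing at baseline only.

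**Cost.** No new data, one extra parameter per predictor, and one reworded sentence. In simulation (n = 50, ICCs 0.5/0.6, four visits) the SD of the person-mean term is about 0.16, against 0.08 for the visit deviation and 0.07 for the single slope. With two visits the three are about 0.15, 0.13 and 0.10. A test of equal slopes has about 48%, 19% and 10% power for within-person slopes 0, 0.2 and 0.3 with four visits, which is why it should not select the model. The working-independence fit has SD about 0.10 and needs a stronger missing-data assumption. Its mean squared error for the same-visit slope is lower than the planned model's at a within-person slope of 0 (0.010 v 0.025), equal at 0.2 (0.010 each) and higher at 0.3 (0.010 v 0.006).
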